4.5. Dose Rationale

The lower dose of FP-02.2 fluoropeptides from the Phase 1 study was chosen for this study. The immunogenicity of this dose was equal to or greater than the immunogenicity of the higher dose in the prior Phase 1 study. The selection of the lower dose is expected to further improve on the safety profile of treatment. Furthermore, with each successive

dose of FP-02.2, a trend toward an increase of the immune responses was observed in this trial. Consequently, treatment has been extended from 3 to 6 doses. It is anticipated that longer treatment will further improve the anti-HBV immune response over time.

4.6. Schedule of Events

The schedule for study activities is presented in Table 1 for the Screening and Treatment Periods and in Table 2 for the Follow-up Period.

 Table 1
 Schedule of Events – Screening and Treatment Periods

Schedule of Ever	Screening Period Treatment Period									
Study Day		Telephone Visit (if needed) ^a	Day 1	Day 8, 36	Day 29	Day 57	Day 85	Day 113	Day 141	Day 169 or ET ^b
Week (s)	-4 to -1		0	7 days after prior visit	4	8	12	16	20	24
Window (days)	_	Up to 3 working days before Day 1	_	±2 days	±2 days	±2 days	±2 days	±2days	±2 days	±2 days
Dose of study medication			1		2	3	4	5	6	
Visit may be conducted at home or work or in part as a telemedicine visit ^c				X						
Informed consent	X									
Eligibility criteria check	X	X	X							
Demographics	X									
Medical history	X									
Concomitant medications (including immunosuppressive medications, vaccines, and new HBV treatments) ^d	X	X	X	X	X	X	X	X	X	X
Complete PE	X									X
Targeted and symptom-driven PE	71		X	X	X	X	X	X	X	11
Height, weight, and BMI	X									X
Vital signs ^e	X		X	X	X	X	X	X	X	X
Fibroscan ^f	X									
ECG e	X									X
Urine pregnancy test ^g	X		X		X	X	X	X	X	X
Drug and alcohol screen	X									
Hepatitis B genotype h	X									
HCV, HDV, and HIV tests	X									
Safety labs °	X		X	X	X	X	X	X	X	X
Liver panel °	X		X	X	X	X	X	X	X	X
HBV serology and viral markers i	X		X				X			X
Whole blood for PBMC isolation			X				X			X
Randomization		Xª	X							
Study medication administration (number)			1		2 j,k,l	3 j,k,l	4 j,k,l	5 j,k,l	6 ^{j,k,l}	
Diary distribution (D) review (R) p			D	R	D	D	RD	RD	RD	R

Screening Period		Treatment Period								
Study Day	Day -35 to Day -4	Telephone Visit (if needed) ^a	Day 1	Day 8, 36	Day 29	Day 57	Day 85	Day 113	Day 141	Day 169 or ET ^b
AEs, including MAEs, NCIs and IMCs, and reactogenicity (systemic and local) ^m	X	X	X	X	X	X	X	X	X	X
Stored blood sample for future analyses ⁿ			X							X

AE = adverse event; BMI = body mass index; ECG = electrocardiogram; ET = early termination; HBV = hepatitis B virus; HCV = hepatitis C virus; HDV = hepatitis delta virus; HIV = human immunodeficiency virus; MAE = medically-attended adverse event; NCI = new-onset chronic illness; IMC = immune-mediated medical condition; PBMC = peripheral blood nonnuclear cell; PE = physical examination; UA = urinalysis

- ^a Randomization may occur up to 3 working days before Day 1 (the day of first dosing) to allow for the possible preparation of study medication by a central pharmacy and shipment to the study site. If the patient is to be randomized before Day 1, the eligibility of the patient will be confirmed by a telephone visit prior to randomization. Concomitant medications AEs will also be assessed.
- b If a patient prematurely discontinues study medication before Day 169, Day 169/Early termination procedures will be performed. Patients who prematurely discontinue study medication will remain in the study for Follow-Up Period study assessments, the dates of visits adjusted to correspond to 13, 26, 39 and 52 weeks after the last dose of study medication.
- ^c A telemedicine visit would include a home visit by appropriate trained personnel to perform a target and symptom-driven physical and obtain vital signs and safety laboratories. The remaining portions of the visit may be conducted virtually by the study investigator.
- d After Day 169 or ET, only immunosuppressive medications, vaccines, and new HBV treatments or medications associated with MAEs, NCIs, SAEs, hepatitis flares, or hepatic injury will be recorded.
- ^e Measured before any blood sample collection.
- f Not required if performed within 12 months or if no fibrosis seen on liver biopsy within 2 years before screening.
- g For women of childbearing potential only. A serum pregnancy test will be obtained in lieu of a urine pregnancy test at screening.
- h Hepatitis B genotyping will be performed at screening if it has not been documented in the prior medical record.
- ¹ Serology and viral markers = HBsAg, anti-HBs, HBVDNA, pg-RNA, HBcAg, HBeAg, HBeAg antibody.
- Jif the patient has experienced an acute illness or temperature > 38°C in the 2 days prior to dosing, the administration of study medication and corresponding visit will be delayed until the illness or fever has resolved.
- k Investigators will review the eligibility of all patients to determine if the next treatment is to be administered. Eligibility for the next treatment will include 1) confirmation that patients did not meet a Stopping Rule (Section 7.1.1); 2) confirmation that the pre-treatment liver parameters are within acceptable ranges for treatment (Section 4.1); 3) confirmation that patients do not have a new confirmed or suspected IMC (Appendix 2). Patients not meeting these criteria will not be treated.
- 1 If an authorized COVID-19 vaccine has been administered in proximity to a scheduled IP administration, a ± 3 day window is allowed for IP dosing.
- ^m After Day 169 or ET, only MAEs, NCIs and IMCs will be recorded.
- ⁿ A single blood sample will be collected for biobanking at the beginning of the study (prior to dosing on Day 1) and end of the study. This sample will be used for future analyses not specified in the protocol. Analysis will be limited to HBV serologic and HBV-specific DNA and RNA and patients' DNA will not be analyzed.
- ° Safety laboratory testing, including liver panel, for Doses 1 and 2 will be obtained during the visits conducted 7±2 days after these doses of study medication. Safety laboratory testing following Doses 3, 4 and 5 will be obtained in the interval from 7 days after dose administration and before the next dose of study medication is administered. Safety labs after Dose 6 will be assessed at the Day 169 visit.
- ^p Diaries will also be reviewed at the Day 85, Day 113, Day 141 and Day 169 visits

Table 2 Schedule of Events – Follow-up Period

	Follow-Up Period					
Study Visit	Day 232	Day 323	Day 414	Day 505 or ET ^a		
Completion of Week (number)	33	46	59	72		
Window (days)	±10 days	±10 days	±10 days	±10 days		
Visit may be conducted at home or work or in part as a telemedicine visit ^b	X		X			
Immunosuppressive medications, vaccines, and new HBV treatments (only) ^c	X	X	X	X		
Targeted and symptom-driven PE	X	X	X	X		
Height and weight				X		
Vital signs ^d	X	X	X	X		
ECG ^d				X		
Hematology and serum chemistry	X	X	X	X		
Liver panel	X	X	X	X		
HBV serology and viral markers ^e		X		X		
Whole blood for PBMC isolation		X		X		
MAEs, NCIs and IMCs (only) ^f	X	X	X	X		

AE = adverse event; ECG = electrocardiogram; ET = early termination; HBV = hepatitis B virus; HIV = human immunodeficiency virus; MAE = medically-attended adverse event; NCI = new-onset chronic illness; IMC = immune-mediated medical condition; PBMC = peripheral blood nonnuclear cell; PE = physical examination.

^a If a patient prematurely discontinues study medication before Day 505, Day 505/Early termination procedures will be performed.

^b A telemedicine visit would include a home visit by appropriate trained personnel to perform a target and symptom-driven physical and obtain vital signs and safety laboratories. The remaining portions of the visit may be conducted virtually by the study investigator.

^c After Day 169 or ET, only immunosuppressive medications, vaccines, and new HBV treatments or medications associated with MAEs, NCIs, SAEs, hepatitis flares, or hepatic injury will be recorded.

^d Measured before any blood sample collection.

^e Serology and viral markers = HBsAg, anti-HBs, HBVDNA, pg-RNA, HBcAg, HBeAg, HBeAg antibody.

f After Day 169 or ET, only MAEs, NCIs and IMCs will be recorded.

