Patients with inactive CHB and over the age of 65 have also been excluded, as they would not be candidates for treatment of their condition in routine clinical practice. There is a global epidemic of obesity and those with hepatitis B are at risk for hepatic steatosis from nonalcoholic fatty liver disease (NAFLD). The risk and prevalence of NAFLD amongst those with HBV appears to be similar as the general population, ranging 17-30% [Shi 2021]. Inclusion of these subjects in the current study is allowed provided there is radiologic evidence of fatty liver or a Fibroscan consistent with hepatic steatosis and no evidence of active CHB (i.e., HBV DNA ≥2000 IU/mL) or other forms of liver disease.

The level of effectiveness and timeframes for contraception use for study eligibility comply with the guidelines of the Clinical Trial Facilitations Group recommendation related to contraception and pregnancy testing in clinical trials [Clinical Trial Facilitation Group 2014]. The fluoropeptides and IC31 of HepTcell are designed to form a local depot at the site of injection, and the magnitude and period of systemic exposure are anticipated to be limited. The high molecular weight peptides that comprise HepTcell present a low risk of passive transmembrane penetration and/or systemic exposure and it is unlikely that they will be absorbed vaginally or placentally. Peptides are expected to be degraded into smaller peptides and individual amino acids by the protein degradation pathways that are well understood. Even if systemic exposure to HepTcell were to occur, the fluoropeptides and IC31 adjuvant components would be rapidly metabolized and their appearance in semen would be limited, as would their appearance in plasma from semen. Any T cells stimulated by HepTcell would also be HBV specific and unable to cross the placenta. Therefore, one-month period of pregnancy testing after the last dose of study medication is considered sufficient to protect patients or their sexual partners who become pregnant after the 6 doses of study medication are administered.

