6.3. Dose and Administration

HepTcell or normal saline placebo will be administered by IM injection at intervals of 4 weeks for 6 doses. Doses will be administered on Days 1, 29, 57, 85, 113, and 141 (±2 days for each dose). The 1.0 mL HepTcell injection contains 0.150 mg of each FP-02.2 peptide and IC31 at 500 nmol KLK and 20 nmol ODN1a.

Each dose of HepTcell or placebo will be administered as an IM injection (1.0 mL) in the deltoid muscle, where possible, of the non-dominant arm by appropriately trained clinical staff members. Patients will stay in the unit for at least 2 hours following administration of the first and second doses. Vital signs will be assessed before dosing and every 15 minutes post dosing over 2 hours at these two visits, and medications and qualified medical personnel will be available in case a patient experiences a severe acute allergic reaction during the immediate post-vaccination period.

Refer to ALT-301-202 Pharmacy Manual for specific preparation information and country specific procedures (if applicable).

If an authorized COVID-19 vaccine has been administered in proximity to a scheduled IP administration, a ± 3 day window is allowed for IP dosing.

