6.7. Prior and Concomitant Therapy

In the interests of patient safety and acceptable standards of medical care, the Investigator will be permitted to prescribe additional treatment(s) at his/her discretion. However, as noted below, changes in any chronically administered medications or treatments should be avoided during the Treatment Period (through Day 169).

All medications must be recorded in the patients' eCRFs from 30 days before the first dose through Day 169 or early termination (ET) from the Treatment Period, but only immunosuppressive medications, vaccines, and new HBV treatments or medications associated with MAEs, NCIs, SAEs, hepatitis flares, or hepatic injury will be recorded beyond this point through the end of the Follow-up Period (Day 505 or ET from Follow-up).

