8.3.2. Adverse Events

Adverse events will be assessed by direct observation and patient assessments/interviews from Screening through the end of study. All AEs will be recorded through the end of the Treatment Period (Day 169 or ET). After that time, only MAEs, NCIs, and IMCs, which will be categorized as AEs, will be recorded through the end of the Follow-up Period (Day 505 or ET). A list of IMCs is provided in Appendix 2.

Details on the definitions, reporting, and management of AEs are provided in Section 9.

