9.2. Reporting Responsibilities and Periods

It is the responsibility of the Investigator or Subinvestigator(s) to perform periodic assessment of AEs. AEs spontaneously reported by the patient or reported in response to an open question from the study personnel (eg, 'Have you had any health problems since the previous visit/you were last asked?') or revealed by observation will be recorded.

AEs and concomitant medications will be recorded from the signing of informed consent to Day 169, but only MAEs, NCIs, and IMCs, which will be categorized as AEs, will be followed subsequently through Day 505. Concomitant medication collection will align with AE collection. The AE term, date of AE onset, date of AE resolution (if applicable), severity, causality, action taken for the AE, outcome and whether or not the AE is an MAE, NCI, and or SAE will be recorded.

AEs must be monitored until they are resolved or stabilized, are clearly determined to be due to a patient's stable or chronic condition or intercurrent illness(es), or follow-up is no longer possible. Data describing AEs will be recorded in the patient's medical record and as appropriate, an SAE report form. SAEs will be reported to the Sponsor as described in Section 9.7.

Any SAE that the Investigator considers to be possibly or probably related to study medication and occurs at any time after completion of the study must be reported to the Sponsor or designee. If at the time the Investigator initially reports an SAE, the event has not resolved, the Investigator must provide a follow-up report as soon as it resolves (or upon receipt of significant information if the event is still ongoing).

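### The protocol gives two different end points for full adverse-event recording, and one of them can leave a patient who stops dosing early with about a week of capture after the last dose

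*Protocol*

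**What the plan says.** **When full AE recording ends.** Two sets of passages differ.

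- Table 1 footnote m, repeated as Table 2 footnote f: "After Day 169 or ET, only MAEs, NCIs and IMCs will be recorded". Section 8.3.2 agrees: "All AEs will be recorded through the end of the Treatment Period (Day 169 or ET".
- Section 9.2: "AEs and concomitant medications will be recorded from the signing of informed consent to Day 169". The Synopsis, section 4.1 and SAP 2.3 say the same, and none of them adds ET.

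**What triggers ET.** Table 1 footnote b, which is attached to the Day 169/ET column, says: "If a patient prematurely discontinues study medication before Day 169, Day 169/Early termination procedures will be performed". Section 7.1 repeats this. Neither sets an interval between the last dose and the ET visit. The patient remains in the study, with "the dates of visits adjusted to correspond to 13, 26, 39 and 52 weeks after the last dose of study medication". Table 2 limits event collection at those visits to MAEs, NCIs and IMCs.

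**Concomitant medication.** The same split appears here. Section 6.7 and footnotes d (Table 1) and c (Table 2) use Day 169 or ET, while 4.1 and 9.2 use Day 169. After the cut-off, section 6.7 still says that "medications associated with MAEs, NCIs, SAEs, hepatitis flares, or hepatic injury will be recorded". That list is wider than the list of events recorded. Section 9.7.2 separately requires every SAE to be reported within 24 hours.

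**Pregnancy testing.** Section 4.4 states that a "one-month period of pregnancy testing after the last dose of study medication is considered sufficient". Table 1 places the last test at Day 169 or ET, and Table 2 has none.

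**The concern.** Because ET follows from stopping the injections and not from leaving the study, the 'or ET' wording ends full AE recording in a patient who is still available for observation. How soon after the last dose this happens is left to when the ET visit is held. A site working from the Schedule of Events and a site working from section 9.2 could therefore record different events for identical patients.

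The analysis does not compensate. SAP 5.3.3.2 counts treatment-emergent AEs from the first dose, sets no end date in days after the last dose, and uses all patients in the safety population of each arm as the denominator. Unequal observation passes straight into the incidence table. Safety is a secondary objective, and patients who stop early are a group in whom complete recording matters.

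**Working it through.** **Inputs.** Section 6.3: "Doses will be administered on Days 1, 29, 57, 85, 113, and 141 (±2 days for each dose". Table 1: Day 169 visit, ±2 days. Section 4.1: safety visits 7±2 days after Doses 1 and 2. Footnote b: follow-up visits at 13, 26, 39 and 52 weeks after the last dose.

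**1. Reproduce the plan's calendar.** 141 + 7 × (13, 26, 39, 52) = Days 232, 323, 414 and 505, as in Table 2. 505 − 1 = 504 days beyond Day 1, as in section 4.1. The timeline is internally correct.

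**2. Completers.** Full recording after the last dose = 169 − 141 = 28 days. With both windows: (169 − 2) − (141 + 2) = 24 to (169 + 2) − (141 − 2) = 32 days.

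**3. Early stoppers, 'or ET' wording.** Full recording = ET date − last dose date. The protocol does not fix the ET date, so two cases are assumed.

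- ET at the 7±2-day visit after Dose 1 or 2: 5 to 9 days. At 7 days this is 7/28 = 25% of the completer window, so 21 of 28 days (75%) are missing. The next scheduled visit is 91 − 7 = 84 days later.
- Stop decided at the next dosing visit, with ET then: about 28 days, no shortfall. The next visit is 91 − 28 = 63 days later.

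**4. Early stoppers, 'to Day 169' wording.** With last dose on day d, full recording = 169 − d, and the first follow-up visit falls on d + 91.

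| Last dose (day) | Full recording after last dose (days) | First follow-up visit (day) |
|---|---|---|
| 1 | 168 | 92 |
| 29 | 140 | 120 |
| 57 | 112 | 148 |
| 85 | 84 | 176 |
| 113 | 56 | 204 |
| 141 (completer) | 28 | 232 |

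A patient whose last dose was on Day 1 has about 7 days under one wording (ET at Day 8) and 168 under the other. For last doses on Days 1, 29 and 57 the first follow-up visit falls before Day 169. There, sections 4.1 and 9.2 call for all AEs, while the Table 2 row calls for three categories only.

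**5. Event list against medication list.** After the cut-off, events are MAEs, NCIs and IMCs. Medications are those linked to MAEs, NCIs, SAEs, hepatitis flares or hepatic injury, plus immunosuppressants, vaccines and new HBV treatments. SAEs, flares and hepatic injury are in the second list only.

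**6. Pregnancy test.** An ET visit 5 to 9 days after the last dose falls short of the one month in section 4.4, and no later test is scheduled.

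**The case against.** The strongest reply is that sections 4.1 and 9.2, the Synopsis and SAP 2.3 already give the fuller rule, under which stoppers are observed for longer than completers. That stands, and it is why the point is a contradiction and not a settled defect. One could try to harmonize the texts by reading ET as leaving the study, but footnote b ties the Day 169/ET column to stopping study medication.

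The timing objection also stands. Nothing requires ET at Day 8 or Day 36. Eligibility is reviewed before each dose, and in two rows of the section 4.1 liver table dosing is interrupted first and discontinuation is raised if the event has not resolved in four weeks or recurs. A short window is possible, not automatic.

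The possible loss is narrow:

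- An MAE includes any non-routine visit to or from medical personnel (9.1.4).
- SAEs have their own reporting route.
- AEs already recorded, including one that led to the stop, are followed until resolved or stabilized (9.2).
- Solicited reactions have a 7-day diary.
- A flare at a scheduled visit appears in the liver panel, and section 9.4 calls for clinically significant laboratory abnormalities to be recorded as AEs without an end date.
- Pregnancies are reportable through Day 505 (9.7.4), so a missed test does not end their capture.

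A reader might infer that the rule understates AE incidence mainly on HepTcell. The documents do not support that. They give no early-stop rate by arm, and section 1.3 reports AE incidence similar to placebo in Phase 1. SAP tables count a patient once per event, so someone stopped for a TEAE already counts under any TEAE and under that term. Only additional new terms could be missed.

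**Conclusion.** The protocol contradicts itself on the end of full AE and concomitant-medication recording for patients who stop dosing but stay in the study. Under the 'or ET' wording, capture after the last dose can range from under one week to about 28 days, against 28 (24 to 32) for completers. Under the 'to Day 169' wording it is 56 to 168 days. The 5-to-9-day figure assumes that ET is done at the 7±2-day visit.

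Only new-onset AEs that are not MAEs, NCIs, IMCs or SAEs are at risk. The number of patients affected is not given, and the direction by arm is unknown. A reader might take the 75% shorter window as 75% of AEs lost. It is a share of observation time after the last dose in one scenario. Turning it into a share of events needs an onset pattern that the documents do not supply.

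The mismatch between the event and medication lists, and between the ET pregnancy test and section 4.4, hold as inconsistencies of the text. This is worth correcting because unequal observation is undesirable in either direction and the correction is cheap. It does not by itself undermine the safety conclusions.

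**What to change.** 1. Reconcile the Synopsis, 4.1, 8.3.2, 9.2, Table 1 footnote m, Table 2 footnote f and SAP 2.3, with the matching medication wording in 6.7 and footnotes c and d, to one rule. Patients who stop dosing but remain in the study have all AEs recorded to Day 169, as 4.1 and 9.2 state, or at minimum to 28 days after the last dose. Add one telephone contact where the ET visit is earlier than the chosen end. If Day 169 is kept, the Table 2 event row must admit all AEs at visits before Day 169.
2. Do not word it as the later of Day 169/ET and 28 days after the last dose. If ET is read as the cut-off for stoppers, that would shorten recording under 4.1 and 9.2 from Day 169 to Day 29 for a patient whose last dose was on Day 1.
3. Add SAEs, hepatitis flares and hepatic injury to the events recorded after the cut-off, so that footnotes m and f agree with the medication list and with 9.7.2.
4. Reconcile the timing of the ET pregnancy test with the one-month period in 4.4.

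The SAP introduction says the Week 24 analysis is done and the study is being terminated. For this trial, the report can therefore state which rule sites followed and tabulate the last-dose-to-ET interval by arm from dates already collected.

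Cost: wording changes, slightly more data entry, and one call for each patient whose ET visit comes early.

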5. POPULATION

5.1. Number of Patients

Approximately 80 patients are planned for enrollment over approximately 24 months at approximately 35 study centers in North America, Europe, UK and Asia-Pacific.

